## F.6 Adverse events

### F.6.1 Definition/classification

For the purposes of the clinical report, Medtronic will classify each Adverse Event according to ISO 14155:2011.\* In case country specific definitions and safety reporting regulations are stricter than mandated per ISO 14155:2011, reporting will be done in compliance with the country specific safety regulations.

All adverse events that meet the study definitions will be reported to the sponsor and documented on the Adverse Event eCRF and in the subject’s medical records.

Clinical events that are inherent to a surgical procedure and expected to occur in the majority of subjects for a projected duration may be considered unavoidable. Such events are listed in Table F-3. These events should not be to be reported as adverse events during this study.

\*: For example, the definition of Serious Adverse Event (SAE) in Germany per the MPSV, § 2 nr 5 is the following:

Serious adverse event is any adverse event, which occurs in an approved clinical investigation or performance evaluation and which has led, might have led or could lead directly or indirectly to the death or any serious deterioration in the state of health condition of a subject, a user or any other person without considering if the event has been caused by the medical device.

**Table F-3: Expected and unavoidable adverse events related to the surgical procedure.**

Description of the Event	Time Frame from the Index Procedure
Endoleaks observed and resolved during	Resolved by the time the subject leaves

the index procedure	the OR
Anesthesia-related nausea and/or vomiting	Within 24 hours
Low-grade fever (< 100° F or < 37.8° C)	Within 48 hours
Back pain related to laying on OR table	Within 72 hours
Incisional pain (pain at access site)	Within 72 hours
Sleep problems or insomnia or post procedural delirium	Within 72 hours
Mild to moderate bruising or ecchymosis	Within 168 hours

Where the definition indicates “device”, it refers to any device used in the study. This might be the device under investigation, or any market released component of the system.

**Adverse Event (AE):** (ISO 14155:2011 3.2)

Any untoward medical occurrence, unintended disease or injury, or untoward clinical signs (including abnormal laboratory findings) in subjects, users or other persons, whether or not related to the investigational medical device

*NOTE 1:* This definition includes events related to the investigational medical device or the comparator.

*NOTE 2:* This definition includes events related to the procedures involved.

*NOTE 3:* For users or other persons, this definition is restricted to events related to investigational medical devices.

**Adverse Device Effect (ADE):** (ISO 14155:2011 3.1)

Adverse event related to the use of an investigational medical device

*NOTE 1:* This definition includes adverse events resulting from insufficient or inadequate instructions for use, deployment, implantation, installation, or operation, or any malfunction of the investigational medical device.

*NOTE 2:* This definition includes any event resulting from use error or from intentional misuse of the investigational medical device

**Serious Adverse Event (SAE):** (ISO 14155:2011 3.37)

Adverse event that

- a) led to death,
- b) led to serious deterioration in the health of the subject, that either resulted in
  - 1) a life-threatening illness or injury, or
  - 2) a permanent impairment of a body structure or a body function, or
  - 3) in-patient or prolonged hospitalization, or
  - 4) medical or surgical intervention to prevent life-threatening illness or injury or permanent impairment to a body structure or a body function,
- c) led to fetal distress, fetal death or a congenital abnormality or birth defect.

*NOTE 1:* Planned hospitalization for a pre-existing condition, or a procedure required by the CIP, without serious deterioration in health, is not considered a serious adverse event.

**Serious Adverse Device Effect (SADE):** (ISO 14155:2011 3.36)

Adverse device effect that has resulted in any of the consequences characteristic of a Serious Adverse Event

**Unanticipated Serious Adverse Device Effect (USADE):** (ISO 14155:2011 3.42)

Serious adverse device effect which by its nature, incidence, severity or outcome has not been identified in the current version of the risk analysis report

*NOTE:* Anticipated serious adverse device effect (ASADE) is an effect which by its nature, incidence, severity or outcome has been identified in the risk analysis report.

**Unanticipated Adverse Device Effect (UADE):** (21CFR812.3)

Any serious adverse effect on health or safety or any life-threatening problem or death caused by, or associated with, a device, if that effect, problem, or death was not previously identified in nature, severity, or degree of incidence in the investigational plan or application, or any other unanticipated serious problem associated with a device that relates to the rights, safety, or welfare of subjects.

*NOTE:* Although the collection of UADEs is a US 21CFR812.3 requirement, any event from the Valiant Evo International Clinical Trial that meets the UADE criteria will be reported as such and will be adjudicated by the Clinical Event Committee (CEC) in order to be pooled with data collected during the concurrently enrolling IDE trial.

**Device deficiency:** (ISO 14155:2011 3.15)

Inadequacy of a medical device with respect to its identity, quality, durability, reliability, safety or performance

*NOTE:* Device deficiencies include malfunctions, use errors, and inadequate labelling.

**For the Valiant Evo International Clinical trial Medtronic has defined Major Device Effects (MDEs) which will be used to assess the primary endpoint.**

MDEs include the occurrence of any of the following and are defined in Appendix L.2.1:

- Device-related secondary procedures
- Device-related mortality
- Conversion to open surgery
- Thoracic aortic aneurysm rupture

**For the Valiant Evo International Clinical trial Medtronic has defined Major Adverse Events which will be used to assess the secondary endpoints.**

MAEs include the occurrence of any of the following and are defined in Appendix L.2.2:

- Respiratory complications: atelectasis, pneumonia, pulmonary embolism, pulmonary edema, respiratory failure.
- Renal complications: renal failure, renal insufficiency.
- Cardiac complications: MI, unstable angina, new arrhythmia, exacerbation of CHF.
- Neurological complications: new cerebrovascular accident (CVA), cerebrovascular embolic events, paraplegia, paraparesis.
- Gastrointestinal complications: bowel ischemia.
- Major bleeding complication (procedural or post-procedural), coagulopathy.
- Vascular complications: aortic rupture, aneurysm rupture, hematoma at access site, pseudo or false aneurysm, arteriovenous (AV) fistula, retroperitoneal bleed, limb ischemia, thrombosis

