***F.6.2 Recording and reporting of Adverse Events***

Adverse Event (AE) information will be collected throughout the study and reported to Medtronic on the Adverse Event eCRF. All Adverse Events (except the ones listed in table F-3), regardless of relatedness or outcome, must be reported. The investigator is responsible for reporting all AE to Medtronic.

See the Adverse Event eCRF for the information to be reported for each Adverse Event.

For Adverse Events that require immediate reporting (see Table F-4), initial reporting may be done by phone, e-mail (contact details will be provided in the investigational site file), or on the eCRF with as much information as is available. In case the investigator requires information from the Sponsor in an emergency situation, the contact details for emergency situations are given in section F.6.7.

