
 
- Access failure
 
- Access site complications (e.g., spasm, trauma, bleeding, rupture, dissection)
 
- Adynamic Ileus
 
- Allergic reaction (to contrast, antiplatelet therapy, stent graft material)
 
- Amputation
 
- Anaphylaxis
 
- Anesthetic complications
 
- Aneurysm expansion
 
- Aneurysm rupture
 
- Angina
 
- Aortic valve damage
 
- Aortic vessel rupture
 
- Arrhythmia
 
- Arterial stenosis
 
- Atelectasis
 
- Blindness
 
- Bowel ischemia
 
- Bowel necrosis
 
- Bowel obstruction
 
- Branch vessel occlusion
 
- Breakage of the metal portion of the device
 
- Buttock claudication
 
- Cardiac tamponade
 
- Catheter breakage
 
- Cerebrovascular accident (CVA)/Stroke
 
- Change in mental status
 
- Coagulopathy
 
- Congestive heart failure
 
- Contrast toxicity
 
- Conversion to surgical repair
 
- Death
 
- Deployment difficulties/failures
 
	
 
- Dissection, perforation, or rupture of the aortic vessel & surrounding vasculature
 
- Embolism
 
- Endoleaks
 
- Excessive or inappropriate radiation exposure
 
- Extrusion/erosion
 
- Failure to deliver the stent graft
 
- Femoral neuropathy
 
- Fistula (including aortoenteric, arteriovenous, and lymph)
 
- Gastrointestinal bleeding/complications
 
- Genitourinary complications
 
- Hematoma
 
- Hemorrhage/bleeding
 
- Hypotension/hypertension
 
- Infection or fever
 
- Insertion or removal difficulty
 
- Intercostal pain
 
- Intramural hematoma
 
- Leg edema/foot edema
 
- Lymphocele
 
- Myocardial infarction
 
- Neuropathy
 
- Occlusion - Venous or Arterial
 
- Pain/Reaction at catheter insertion site
 
- Paralysis
 
- Paraparesis
 
- Paraplegia
 
- Paresthesia
 
- Peripheral ischemia
 
- Peripheral nerve injury
 
- Pneumonia
 
- Postimplant syndrome
 
	
 
- Post-procedural bleeding
 
- Procedural bleeding
 
- Prosthesis dilatation
 
- Prosthesis infection
 
- Prosthesis rupture
 
- Prosthesis thrombosis
 
- Pseudoaneurysm
 
- Pulmonary edema
 
- Pulmonary embolism
 
- Reaction to anesthesia
 
- Renal failure
 
- Renal insufficiency
 
- Reoperation
 
- Respiratory depression or failure
 
- Retrograde type A dissection
 
- Sepsis
 
- Seroma
 
- Shock
 
- Spinal neurological deficit
 
- Stent graft migration
 
- Stent graft misplacement
 
- Stent graft occlusion
 
- Stent graft twisting or kinking
 
- Transient ischemic attack (TIA)
 
- Thrombosis
 
- Tissue necrosis
 
- Vascular ischemia
 
- Vascular trauma
 
- Wound dehiscence
 
- Wound healing complications
 
- Wound infection
 

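### Table F-3 exempts listed post-procedure events from AE reporting with no exception for serious ones, in conflict with the SAE definition and Table F-4

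*Protocol*

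**What the plan says.** Protocol F.6.1 introduces Table F-3. The stated basis is that events which come with surgery and are "expected to occur in the majority of subjects for a projected duration may be considered unavoidable". The instruction to sites follows: "These events should not be to be reported as adverse events during this study". F.6.2 repeats it within the general reporting duty: "All Adverse Events (except the ones listed in table F-3), regardless of relatedness or outcome, must be reported".

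One row of Table F-3 reads "Sleep problems or insomnia or post procedural delirium", with a time frame of 72 hours from the index procedure. Another reads "Mild to moderate bruising or ecchymosis".

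F.6.1 then defines an SAE as an adverse event that led to death, to fetal harm, or to serious deterioration in the subject's health with one of four results. One of the four is "in-patient or prolonged hospitalization". Table F-4 requires investigators to send SAEs to the sponsor within 3 calendar days of learning of them, and sets the same limit for ADEs and SADEs. None of these rows mentions Table F-3.

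**The concern.** The exemption depends on the type of event and its timing. Whether the case was serious plays no part. A listed event can therefore meet the SAE definition while F.6.1 and F.6.2 tell the site not to report it.

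Two things would be at stake. The first is the secondary endpoint of all AEs within 30 days, including SAEs (C.2.2.1), together with the 365-day count that contains those days (C.2.2.2). The second is ongoing safety review, which works from reported events. This is a first-in-human study, and J.2 says that not all risks may be known. An exemption applied at source is hard to undo later.

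**Working it through.** The plan states no figure to reproduce, so the check compares the passages and ends with one piece of arithmetic for scale.

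**1. How each Table F-3 row is bounded**

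| Listed event | Time frame | Other limit |
|---|---|---|
| Endoleak during the procedure | until leaving the OR | must have resolved |
| Nausea or vomiting | 24 h | cause (anesthesia) |
| Fever | 48 h | severity (below 37.8 °C) |
| Back pain | 72 h | cause (OR table) |
| Incisional pain | 72 h | location (access site) |
| Sleep problems, insomnia, delirium | 72 h | none beyond being post-procedural |
| Bruising | 168 h | severity (mild to moderate) |

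Only the fever and bruising rows limit severity. The delirium row is in effect limited by time alone. The table does not say whether its hours refer to onset or to duration.

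**2. Can a listed event be an SAE?** Yes. The AE definition in F.6.1 includes procedure-related events, and the title of Table F-3 itself calls its entries adverse events. The relevant SAE limb needs two elements: serious deterioration in health, and a result such as "in-patient or prolonged hospitalization" or intervention to prevent a life-threatening illness or permanent impairment. Delirium in the first 72 hours can satisfy both.

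**3. Which rule then applies?** F.6.1 and F.6.2 exempt the event. Table F-4 requires it within 3 calendar days. Neither F.6.1, F.6.2, Table F-3, Table F-4 nor the SAP restores reporting for serious cases or ranks the two rules.

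**4. Where would a withheld event be missed?** SAP 7.10 takes seriousness from the site's AE form, so an event never entered there cannot be counted as an SAE. Under protocol F.6.7 the Independent Medical Monitor receives monthly listings of AEs and device deficiencies and can trigger a DMC meeting. A withheld event is not in those listings.

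**5. What is not affected?** The primary endpoint rests on access or deployment failure and MDEs. Under F.6.6 the CEC adjudicates MDEs and all deaths. Neither the primary endpoint nor mortality depends materially on Table F-3.

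**6. Scale.** The input is 47 included subjects (protocol C.7). If one subject's only SAE within 30 days is withheld, the SAE proportion falls by

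1 / 47 = 0.0213, or 2.1 percentage points.

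This takes all 47 as evaluable. If the subject has another SAE in the period, the proportion does not change. The documents give no rate of delirium or of serious Table F-3 events, so the number of such subjects cannot be derived.

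**The case against.** The strongest reply is that the text does not make omission certain. Table F-4 sets free-standing duties with no Table F-3 exception, and a site may well follow it. Table F-4 and the text after it also oblige investigators to report under EC and local rules, and F.6.1 lets stricter national rules prevail. E.3 says that where requirements conflict, the regulation most protective of the subject is followed. This stands in part: withholding is possible, not established. But local rules vary by country, and E.3 speaks of regulations, not of two sections of the same protocol. Uneven reporting across up to 17 sites would itself weaken the endpoint.

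It can also be said that part of the remedy is already implied. The exemption refers to a projected duration and listed hours, and device-related events have their own rows in Table F-4. That is a fair reading, but the table leaves the hours undefined and F.6.2 applies its exception without regard to relatedness.

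A reader might infer more than the documents support:

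- **That any delirium prolonging the stay is an SAE.** The definition also requires serious deterioration in health.
- **That a neurological signal would be missed.** New CVA, cerebrovascular embolic events, paraplegia and paraparesis are named MAEs and are not in Table F-3, so a diagnosed event stays reportable. The documents do not say that confusion precedes such events.
- **That Table J-1 contradicts Table F-3 by listing "Change in mental status".** Table J-1 lists possible risks, including endoleaks, fever and insertion-site pain, which overlap other Table F-3 rows. It does not set reporting rules.
- **That a definite number of SAEs would be lost.** Any such figure needs assumed rates of delirium and of serious cases.
- **That delirium must be struck from the list.** Whether it occurs in most subjects, as the basis for the list requires, is open to question. Removing it is still a preference. SAP 7.3 assumes poolability with the US trial partly because event definitions are similar, and that protocol is not available here. A deletion in this trial alone could make AE capture differ.

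**Conclusion.** The concern holds as an unresolved conflict between the Table F-3 exemption on one side and the SAE definition with Table F-4 on the other. Followed as written, F.6.1 and F.6.2 could keep a listed event that meets the SAE definition off the AE form, and so out of the 30-day and 365-day AE/SAE secondary endpoints and the medical monitor's listings. Sites could also resolve the conflict differently. It does not follow that SAEs are in fact being left out.

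The effect is limited to AE/SAE secondary endpoints and AE-based safety review. All endpoints are descriptive with no pass/fail criterion (C.3), so no test result is at risk. The size is 2.1 percentage points of the SAE proportion for each subject whose only SAE is withheld, assuming 47 evaluable subjects. The total cannot be estimated from the documents.

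**What to change.** Reconcile F.6.1, Table F-3, F.6.2 and Table F-4 by adding one sentence to Table F-3 and to F.6.2, for example:

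*The exemption does not apply to an event that meets the SAE definition, is related to the device, or lasts beyond the stated time frame; such events are reported under Table F-4.*

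Check the corresponding wording in the US trial's protocol, so that AE capture stays comparable in the pooled analysis.

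The cost is one sentence in two places, a reminder to sites, a few more AE forms and possibly a slightly higher SAE count. The change concerns reporting only and leaves clinical management as it is.

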***F.6.2 Recording and reporting of Adverse Events***

Adverse Event (AE) information will be collected throughout the study and reported to Medtronic on the Adverse Event eCRF. All Adverse Events (except the ones listed in table F-3), regardless of relatedness or outcome, must be reported. The investigator is responsible for reporting all AE to Medtronic.

See the Adverse Event eCRF for the information to be reported for each Adverse Event.

For Adverse Events that require immediate reporting (see Table F-4), initial reporting may be done by phone, e-mail (contact details will be provided in the investigational site file), or on the eCRF with as much information as is available. In case the investigator requires information from the Sponsor in an emergency situation, the contact details for emergency situations are given in section F.6.7.

### F.6.3 Recording and reporting of Device Deficiencies

Device Deficiency information will be collected throughout the study and reported to Medtronic. Device Deficiencies should be reported on a Device Deficiency Form in the eCRF. In case the eCRF is not available the Device Deficiency form needs to be completed manually and must be sent to Medtronic. Contact details are given in the investigational site file. The investigator is responsible for reporting all Device Deficiencies to Medtronic.

See the Device Deficiency eCRF for the information to be reported for each Device Deficiency.

Device deficiencies that did not lead to an Adverse Event but could have led to an SAE

- a) if either suitable action had not been taken,
- b) if intervention had not been made, or
- c) if circumstances had been less fortunate,

require immediate reporting (see Table F-4). Initial reporting may be done by eCRF, phone, e-mail, with as much information as available.

### F.6.4 Adverse Event and Device Deficiency review process

All Adverse Events and Device Deficiencies will be reviewed by Medtronic Study Management and/ or designee. This review will include the determination whether the Adverse Event/Device Deficiency meets regulatory reporting requirements (see table F-4). The sponsor will ensure timely Adverse Event/Device Deficiency reporting to meet global and country specific regulatory requirements.

A list of anticipated adverse events that are expected in nature is included in section J.2.

**Table F-4: Adverse Event Reporting Requirements**

Serious Adverse Device Effects (SADE), including Unanticipated Serious Adverse Device Effect (USADE):	
Investigator submit to:	
Medtronic	As soon as possible, but in no case later than 3 calendar days after the clinical site study team first learns of the event or of new information in relation with an already reported event.
Regulatory Authority	As per local reporting requirement
EC	Reporting timeframe as per local EC requirement.
Sponsor submit to:	
Regulatory Authorities	Reporting timeframe as per local requirement.
EC	Submit to EC per local reporting requirement.
Serious Adverse Events (SAE)	
Investigator submit to:	
Medtronic	As soon as possible, but in no case later than 3 calendar days after the clinical site study team first learns of the event or of new information in relation with an already reported event.
Regulatory Authority	As per local reporting requirement
EC	Submit to EC per local reporting requirement.
Sponsor submit to:	

Regulatory Authorities	Reporting timeframe as per local requirement.
EC	Submit to EC per local reporting requirement.
Adverse Device Effects (ADE)	
Investigator submit to:	
Medtronic	As soon as possible, but in no case later than 3 calendar days after the clinical site study team first learns of the event.
Regulatory Authority	As per local reporting requirement
EC	Submit to EC per local reporting requirement.
Sponsor submit to:	
Regulatory Authorities	Reporting timeframe as per local requirement
EC	Submit to EC per local reporting requirement.
All other AEs	
Investigator submit to:	
Medtronic	Submit in a timely manner after the clinical site study team first learns of the event.
Regulatory Authority	As per local reporting requirement
EC	Submit to EC per local reporting requirement.
Device Deficiency with SADE potential	
Investigator submit to:	
Medtronic	As soon as possible, but in no case later than 3 calendar days after the clinical site study team first learns of the deficiency or of new information in relation with an already reported deficiency.
Regulatory Authority	As per local reporting requirement
EC	Submit to EC per local reporting requirement.
Sponsor submit to:	
Regulatory Authorities	Reporting timeframe as per local requirement
EC	Submit to EC per local reporting requirement.
All other Device Deficiencies	
Investigator submit to:	
Medtronic	Submit in a timely manner after the clinical site study team first learns of the deficiency.
Regulatory Authority	As per local reporting requirement
EC	Submit to EC per local reporting requirement.

In addition, Investigators are obligated to report adverse events in accordance with the requirements of their EC and local regulations. The Sponsor is obligated to report adverse events and device deficiencies that occur during this trial to the Regulatory Authorities and EC as per local requirements.

### *F.6.5 Potential Complaint Reporting*

Potential complaints sourced from the study are reported to the Global Complaint Handling Unit (GCH)

Potential complaints may be found throughout clinical study data as reported on CRFs and reviewed, or potential complaints may be learned about in alternative fashions within source documents or in discussions with investigational site staff. Potential complaints are considered for the following:

- All adverse events collected deemed related to the procedure/product/therapy
- All product deficiencies or technical observations, if applicable
- All deaths deemed related to the procedure/product/therapy

Relationship is to be determined by the investigator and the sponsor. The CEC will assess relationship for adjudicable events only.

